for the second consecutive blood glucose value >150 mg/dL but ≤ 300 mg/dL and continue per protocol for a maximum duration of 48 hours. Exenatide will be administered by intravenous infusion (50 ng/min for 30 minutes, then start exenatide infusion 25 ng/min) for the second consecutive blood glucose value >150 mg/dL but ≤ 300 mg/dL and continue per protocol for a maximum duration of 48 hours (dose, route, titration schedule, and duration). Exenatide will be prepared by the Investigational Drug Service. The exenatide infusion initiation and maintenance protocols are outlined in Tables 1&2 of the attached study protocol. The exenatide infusion blood glucose goal will be 110-180 mg/dL. During the exenatide infusion, glucose measurements will be obtained hourly. The exenatide infusion will be temporarily discontinued for blood glucose <110 mg/dL. The exenatide infusion will be restarted once the blood glucose level is at least 110 mg/dL. Episodes of hypoglycemia will be treated according to the following guidelines: 1) glucose <70 mg/dL will be provided 25 mL of dextrose 50% (1/2 amp) 2) blood glucose will be re-checked in 5 minutes; if mental status changes caused by hypoglycemia are not reversed or blood glucose remains <70 mg/dL, the above dextrose administration will be repeated, 3) serum glucose will be checked hourly after dextrose administration and the episode has resolved. Exenatide infusion will be restarted beginning with the second hourly glucose check that is ≥ 110 mg/dL. Insulin sensitive sliding scale using formulary rapid acting insulin will be used for blood glucose 181-300 mg/dL starting at the 2nd hourly glucose check (≥ 2 hours since exenatide initiation). The physician will be notified for any blood glucose >300 mg/dL for initiation of a rescue insulin infusion protocol. All glucose values will be documented in the ICU Electronic Documentation System.

Table 1: Exenatide Infusion Initiation Protocol

Glucose (mg/dL)	Action
151-300	
Give exenatide 50 ng/min for 30 minutes, then start exenatide infusion 25 ng/min
 
Give prokinetic agent per NSICU protocol (reglan, erythromycin, etc)
 
Check glucose hourly
 
Monitor blood pressure continuously during exenatide infusion. If SBP <100 mmHg, contact physician. Decision to discontinue exenatide infusion will be made at the discretion of the treating physician.

Table 2: Exenatide Infusion Maintenance Protocol

Glucose (mg/dL)	Action

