<70	
Discontinue exenatide infusion.
 
Give 25 mL of dextrose 50% (1/2 amp) IVP – Recheck glucose in 5 minutes and notify physician.
 
Check glucose hourly after hypoglycemia is resolved.
 
When 2 in a row hourly glucose checks are greater than 109 restart exenatide infusion at 25 ng/min
 
Notify physician when glucose greater than 80 mg/dL
 
Monitor blood pressure continuously during infusion (if SBP <100 mmHg, contact physician)

80-109	
Temporarily discontinue exenatide infusion
 
Check glucose hourly
 
When glucose greater than 109 restart exenatide infusion at 25 ng/min
 
Note: If 3 in a row hourly checks are less than 110 restart protocol from beginning. Change glucose check to q4h and exenatide protocol for second glucose greater than 180 mg/dL
 
Monitor blood pressure continuously during infusion (if SBP <100 mmHg, contact physician)

110-180	Continue exenatide infusion per protocol Check glucose hourly Monitor blood pressure continuously during infusion (if SBP<100 mmHg, contact physician)
181-216	1 st hourly glucose check (=1 hour since exenatide initiation): continue exenatide infusion protocol ≥2 nd hourly glucose check (≥2 hours since exenatide initiation): Give 2 units of formulary available rapid acting insulin subcutaneously and continue exenatide infusion protocol Check glucose hourly Monitor blood pressure continuously during infusion (if SBP <100 mmHg, contact physician)
217-252	1 st hourly glucose check (=1 hour since exenatide initiation): continue exenatide infusion protocol ≥2 nd hourly glucose check (≥2 hours since exenatide initiation): Give 4 units of formulary available rapid acting insulin subcutaneously and continue exenatide infusion protocol Check glucose hourly Monitor blood pressure continuously during infusion (if SBP <100 mmHg, contact physician)
253-300	1 st hourly glucose check (=1 hour since exenatide initiation): continue exenatide infusion protocol ≥2 nd hourly glucose check (≥2 hours since exenatide initiation): Give 6 units of formulary available rapid acting insulin subcutaneously and continue exenatide infusion protocol Check glucose hourly Monitor blood pressure continuously during infusion (if SBP <100 mmHg, contact physician)
>300	Recheck blood glucose within 5 minutes If confirmed, contact physician to discontinue exenatide and initiate rescue insulin infusion protocol (NSICU insulin infusion protocol)

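### After three consecutive low glucose readings the protocol text and the Table 2 note give different restart rules, and Table 2 has no row for 70-79 mg/dL

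*Combined protocol and SAP*

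**What the plan says.** Three places govern what happens to the infusion after low readings.

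- **Text of Methodology item 2, Glycemic Control Protocol.** Exenatide is started "for the second consecutive blood glucose value >150 mg/dL", with an upper limit of 300 mg/dL. It is paused below 110 mg/dL and resumed once glucose is at least 110. Dextrose is given only below 70, and after such an episode the restart waits for the second hourly check at or above 110. The text adds: "The exenatide infusion initiation and maintenance protocols are outlined in Tables 1&2".
- **Table 1 (initiation).** For 151-300 mg/dL: "Give exenatide 50 ng/min for 30 minutes, then start exenatide infusion 25 ng/min".
- **Table 2 (maintenance).** The first row is below 70 and the next is 80-109. The 80-109 row pauses the infusion and gives an ordinary restart rule: "When glucose greater than 109 restart exenatide infusion at 25 ng/min". A note in the same row then says: "If 3 in a row hourly checks are less than 110 restart protocol from beginning". Its next sentence reads: "Change glucose check to q4h and exenatide protocol for second glucose greater than 180 mg/dL".

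The row for values below 70 has its own restart rule, "When 2 in a row hourly glucose checks are greater than 109 restart exenatide infusion at 25 ng/min", and its own cue: "Notify physician when glucose greater than 80 mg/dL".

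**The concern.** A patient who has just had three low readings in a row is in a state where the infusion rules need to be unambiguous. Here, staff working from the text and staff working from the Table 2 note could act differently on the same value, and the plan gives no order of precedence between them.

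Continuous glucose monitoring cannot settle the matter at the bedside. Under Methodology item 3, nursing staff are blinded to it, and treatment decisions rest on standard glucose monitoring under the glycemic control protocol.

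This matters for the study as well as for the patient. It is a single-arm feasibility trial in 24 patients, and the infusion protocol is the thing being tested. If its rules are applied in more than one way, the results describe a mixture of delivery rules that nobody chose.

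The missing 70-79 row is a smaller matter of the same kind. Outcomes section 10.2 counts any value below 80 mg/dL as hypoglycemia, so the unlisted band lies within a range that the plan itself monitors.

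**Working it through.** The plan states no figure to reproduce. The check sets the rules side by side and counts the whole-number glucose values (mg/dL) on which they differ.

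**1. Restart after three consecutive hourly checks below 110**

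| Source | Glucose needed | Readings needed | Check interval | Starting step |
|---|---|---|---|---|
| Text, Methodology item 2 | at least 110 | one | hourly during infusion | rate not given in the restart rule |
| Table 2 note, first sentence, taken back to the text and Table 1 | above 150, up to 300 | two consecutive | not given | Table 1's opening step, if taken literally |
| Table 2 note, second sentence | above 180 | a second one | every 4 hours | not given |

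**2. Text against note.** The text resumes on one reading of at least 110. The note waits for a second reading above 180, with checks every 4 hours, so its two qualifying readings are at least 4 hours apart. The text has no exception for three lows, so these rules conflict directly.

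**3. Note against the rule it points to.** The note gives no upper limit; I assume 300, as in Table 1.

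- Second readings that trigger under the initiation rule: 151 to 300, which is 300 - 151 + 1 = 150 values.
- Second readings that trigger under the note's second sentence: 181 to 300, which is 300 - 181 + 1 = 120 values.
- Difference: 150 - 120 = 30 values, namely 151-180.

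For a second reading in 151-180, starting over under the initiation rule gives exenatide, and the note's stated trigger does not.

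**4. Starting step.** The 80-109 row's ordinary restart is at 25 ng/min. Table 1 opens at 50 ng/min for 30 minutes. The note sends the reader to the beginning without saying whether that opening step is repeated.

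**5. Coverage of Table 2.** The rows are below 70, 80-109, 110-180, 181-216, 217-252, 253-300 and above 300. The only values without a row are 70 to 79, which is 79 - 70 + 1 = 10 values. All ten fall under the text's pause below 110, none under its dextrose rule below 70, and all under the below-80 definition in Outcomes section 10.2.

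**6. Where the sources agree.** For whole-number readings, above 109 and at least 110 are the same condition. The ordinary restart in the 80-109 row therefore matches the text, and so does the two-check restart after a value below 70. The inconsistency is confined to the three-low state and the missing row.

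**The case against.** The best defence is that the note is one coherent instruction: go back to the state before initiation, now with 4-hourly checks and a re-entry trigger of a second value above 180. On that reading the second sentence qualifies the first. The threshold of 150 does not appear in the note; it comes from the text and Table 1. This stands, and for that reason I do not say that the note contradicts itself, though a reader might infer it. But no other place says that re-initiation uses a different threshold, and the text's restart at 110 still conflicts. The text does refer to the tables, but it also states its own unqualified restart rule and gives neither source priority.

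Four further inferences are tempting but not supported.

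- **That 70-79 is left without instruction.** The text pauses the infusion there and reserves dextrose for values below 70. Nor is the lack of a physician call at 70-79 shown to be an omission, since the 80-109 row has no glucose-based call either. The association between a nadir below 80 and poor outcome, cited under Specific Aim 3, comes from an observational study of intensive insulin after subarachnoid hemorrhage. It does not show harm from a missing row.
- **That 71 values get conflicting answers.** This adds 110-150 (150 - 110 + 1 = 41) to the 30 above, and so mixes a one-reading rule with a two-reading rule. On a first reading alone, the text and the note differ over all of 110-300 (300 - 110 + 1 = 191). The 30 values compare like with like.
- **That there is a twofold dose conflict.** Table 1's opening half hour delivers 50 x 30 = 1,500 ng, against 25 x 30 = 750 ng under the ordinary restart. But the ordinary restart belongs to a patient without three lows. The note is silent on the step; the documents do not give two doses for one state.
- **That hourly measurement in Methodology item 8 is contradicted, or that the endpoints are biased.** Item 8 cites Table 2, and the note applies while the infusion is held. An effect on the descriptive below-80 ratio would require blood glucose to be its source, which is not stated, and no feasibility criterion uses that ratio.

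**Conclusion.** The concern holds as a limited internal inconsistency that should be corrected. After three consecutive hourly checks below 110 mg/dL, the text and the Table 2 note give different restart conditions. The note's trigger also differs from the initiation rule it invokes for a second reading of 151-180 mg/dL, and the note leaves the starting step open. Table 2 lacks a row for 70-79 mg/dL, but the text supplies the pause, so this is a defect of the table only.

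The count of 30 assumes whole-number readings and an upper limit of 300 mg/dL. The finding also assumes that the rows of Table 2 are complete as printed; nothing suggests a lost row. The documents do not say how often the three-low state would arise, so the effect on patients or results cannot be sized. Nothing here shows that a feasibility criterion is wrong.

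**What to change.** Reconcile the text of Methodology item 2, Table 1 and Table 2 so that:

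- every glucose value falls in exactly one row of Table 2;
- the restart condition, starting step and check interval after repeated low readings are stated identically in all places.

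Which threshold, step and interval apply is for the clinical team to decide; this review takes no position on it.

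The cost is a clarification amendment and a matching update to any order set. It needs no added patients or procedures.

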6. General Management Protocol: All patients will be managed using standard NSICU protocols. ICP will be kept < 25 mmHg using a stepwise management strategy (management strategies will be recorded). Patients fluid will be maintained with crystalloids without glucose and enteral nutrition will be started as soon as possible. No patients will receive intravenous or oral steroids for their brain injury. Seizure prophylaxis will be provided per protocol for 7 days and sedation/analgesia will be provided as needed and titrated to standard monitoring scales or ICP. A prokinetic agent will be initiated for study subjects per NSICU protocol. Blood pressure will be monitored continuously throughout the study period for all subjects. All medications received during study drug infusion will be recorded.

7. Safety Data:

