1.6 Other Safety Considerations

Any significant worsening noted during interim or final physical examinations, electrocardiograms, x-rays, and any other potential safety assessments, whether or not these procedures are required by the protocol, should also be recorded as a nonserious or serious AE, as appropriate, and reported accordingly.

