2 DATA MONITORING COMMITTEE AND OTHER EXTERNAL COMMITTEES

Not applicable

8. Measurements: Blood glucose from the arterial line will be measured at baseline (prior to exenatide), hourly during the 48 hour exenatide infusion per protocol (table 2) and continue for an additional 24 hours following exenatide discontinuation. The continuous glucose monitor will measure the interstitial glucose level every 5 minutes beginning at baseline (prior to exenatide) until 24 hours following exenatide discontinuation. Blood samples for pharmacokinetic analysis will be collected in serum separator tubes at 0, 12, 24, 36 and 48 hours after the start of the infusion. Eight-hour urine collections will be obtained on a daily basis for 72 hours (48 hours during study drug infusion and an additional 24 hours during follow-up after study drug is discontinued). Microdialystate concentrations will be collected at baseline (prior to exenatide), and hourly during the 48-hour exenatide infusion for parameters of energy metabolism (glucose, pyruvate, lactate, lactate:pyruvate ratio), glutamate (marker of cerebral ischemia), and glycerol (marker of cell membrane degradation) and for an additional 24 hours following study drug discontinuation. Blood pressure will be measured continuously throughout the study period. Intracranial pressure (ICP) will be measured continuously during the exenatide infusion. Intracranial pressure values will be recorded at baseline (prior to exenatide) and daily mean ICP and cerebral perfusion pressure values will be reported. Baseline demographic information (e.g. gender, age, ethnicity) and disease severity information [e.g. Glasgow coma score, SOFA score (Sequential Organ Failure Assessment), Hunt Hess classification, Fisher grade, primary diagnosis, past medical history (including measurement of hemoglobin A1c), neurologic exam/computed tomography scan abnormalities] will be collected. The ICU day of study drug administration will be recorded and the total hospital and ICU lengths of stay will be recorded.

9. Data Management: Each participant will be assigned a unique identification number. No personal identification will be used. All study files will be stored in locked cabinets in the Principal Investigator's office in the Pharmacy Administration Department. Data will be entered into the study database using double entry (entry and verification) and will be checked for missing or ineligible responses.

10. Outcomes

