10.1 The following feasibility endpoints are based upon prior literature (Nice-Sugar and Exenatide Study in the Cardiac ICU):

Proportion of patients experiencing severe hypoglycemia (<40 mg/dL), Proportion of patients achieving plasma glucose goal (110-180 mg/dL), Proportion of patients experiencing nausea requiring discontinuation of exenatide therapy

10.2 The following descriptive endpoints are included for describing experience with exenatide use in the NSICU population:

Average blood glucose value during exenatide infusion (48 hours), percent time in glucose range (48 hours), mean time to reach plasma glucose goal (110-180 mg/dL), variability outcome (SD)-MADGE, mean insulin use required (units/kg body weight), proportion of subjects requiring rescue insulin infusion protocol, number of hypoglycemic episodes (<80 mg/dL)/total number of glucose measurements (48 hours), number of subjects with >1 hypoglycemic episode (<80 mg/dL)/total number of subjects (48 hours), correlation of exenatide concentrations with creatinine clearance during infusion, elimination rate constant and area under the concentration-time curve utilizing concentrations after discontinuation of infusion, side effects and adverse events (AEs and SAEs), average daily ICP and CPP during study drug infusion, number of hypotensive episodes (SBP<100 mmHg) (48 hours), number of subjects with >1 hypotensive episode/total number of subjects (48 hours). Other adverse effects will be collected specifically assessing any alterations in gastric motility.

In patients receiving invasive intracranial multimodal monitoring as part of their standard of care, the following endpoints associated with exenatide use will be described:

Percent time outside of range for energy metabolism (glucose <0.7 mmol/L and lactate:pyruvate ratio > 40), glutamate (marker of cerebral ischemia), and glycerol (marker of cell membrane degradation) parameters (48 hours).

Based upon prior literature, the prespecified criteria for determining feasibility include the following: 1) no more than 6 patients (25%) experiencing severe hypoglycemia (<40 mg/dL); 2) at least 18 patients (75%) achieving the plasma glucose goal (110-180 mg/dL); 3) no more than 6 patients (25%) experiencing nausea leading to exenatide discontinuation. These criteria will be utilized to determine whether a future efficacy trial will be pursued.

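### The only ICP-specific outcome is the daily mean under ICP-directed therapy, so rises met by escalation can be partly or largely masked; the recorded therapy should be summarised beside it

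*Combined protocol and SAP*

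**What the plan says.** Item 6 (General Management Protocol) sets a ceiling for ICP and a way of holding it: "ICP will be kept < 25 mmHg using a stepwise management strategy (management strategies will be recorded". The same item says that "sedation/analgesia will be provided as needed and titrated to standard monitoring scales or ICP", and that "All medications received during study drug infusion will be recorded".

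Item 8 (Measurements) says "Intracranial pressure (ICP) will be measured continuously during the exenatide infusion", and then "Intracranial pressure values will be recorded at baseline (prior to exenatide) and daily mean ICP and cerebral perfusion pressure values will be reported". Section 10.2 lists as a descriptive endpoint "average daily ICP and CPP during study drug infusion".

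Section 10.2 contains no count of ICP episodes, no time above a threshold and no measure of the therapy used to control ICP. Item 12 (Data analysis plan) does not mention the recorded strategies. None of the three feasibility criteria at the end of item 10 involves ICP.

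A general route also exists. Section 10.2 lists "side effects and adverse events (AEs and SAEs", and section 1.6 of the safety text asks that the following be recorded as an adverse event: "Any significant worsening noted during interim or final physical examinations, electrocardiograms, x-rays, and any other potential safety assessments". No ICP value and no escalation of ICP therapy is named as reportable.

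**The concern.** During the infusion ICP is a controlled quantity. When it approaches or passes the ceiling, staff add therapy, and the pressure recorded afterwards reflects both the underlying tendency and that therapy. If the tendency worsens, part of the change appears as more therapy rather than as higher pressure. A daily mean of the treated trace captures only the remainder.

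The plan already handles this for glucose. Section 10.2 reports average glucose together with insulin use per kg of body weight and the proportion of subjects who need the rescue insulin infusion. A reader can then see how much added treatment lay behind the glucose values. ICP has no such companion, although the strategies are to be recorded.

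At stake is one descriptive statement in the study report. ICP and CPP could be described as stable on exenatide in patients who needed additional steps to remain so, and that description could be carried into the planning of a later trial.

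**Working it through.** The documents state no ICP mean, SD, event rate or margin, so there is no planned figure to reproduce. The check first compares the text and then gives two illustrations in which every ICP input is assumed, apart from the 25 mmHg ceiling.

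**Text comparison**

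| Quantity | Recorded? | In an outcome or analysis? |
|---|---|---|
| ICP before infusion | Yes (item 8) | Not as an outcome; available as a reference |
| ICP during infusion | Yes, continuously (item 8) | Daily mean only (item 8, section 10.2) |
| ICP management strategies | Yes (item 6) | No |
| Medications during infusion | Yes (item 6) | Insulin only (section 10.2) |
| ICP therapy or medications just before infusion | Not stated | No |

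**Illustration 1: dilution in a 24-hour mean**

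Shift in daily mean = (peak − baseline) × minutes ÷ 1440.

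- Peak 30, baseline 18, one 30-minute episode: (30 − 18) × 30 ÷ 1440 = 0.25 mmHg.
- Peak 40, baseline 12, one 30-minute episode: (40 − 12) × 30 ÷ 1440 = 0.58 mmHg.
- Four such episodes in a day: 4 × 0.25 = 1.0 mmHg and 4 × 0.58 = 2.3 mmHg.

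Short episodes that are promptly treated barely move the planned summary.

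**Illustration 2: pressure under a treatment ceiling**

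ICP was simulated for 48 hours in 30-minute intervals, with 2,000 patients per scenario. Assumptions: within-patient SD 3 mmHg; autocorrelation 0.8; a sustained rise of 0, 5 or 10 mmHg phased in over the first 6 hours; one therapy step added whenever ICP reaches 25 mmHg; each step lowers ICP by 4 mmHg and is not withdrawn. Means are over the second 24 hours; escalations are over the full 48 hours.

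| Baseline | Assumed rise | Untreated mean | Treated mean | Escalations per patient | Patients with any escalation |
|---|---|---|---|---|---|
| 18 | 0 | 18.02 | 16.73 | 0.40 | 40% |
| 18 | 5 | 23.00 | 17.11 | 1.63 | 100% |
| 18 | 10 | 28.03 | 17.03 | 2.90 | 100% |
| 15 | 0 | 14.95 | 14.89 | 0.03 | 3% |
| 15 | 5 | 19.98 | 17.04 | 0.91 | 83% |
| 15 | 10 | 24.97 | 17.03 | 2.13 | 100% |

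Share of the rise that stays visible = (treated mean with rise − treated mean without rise) ÷ rise:

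- Baseline 18, rise 5: (17.11 − 16.73) ÷ 5 = 0.38 ÷ 5 = 8%.
- Baseline 18, rise 10: (17.03 − 16.73) ÷ 10 = 0.30 ÷ 10 = 3%.
- Baseline 15, rise 5: (17.04 − 14.89) ÷ 5 = 2.15 ÷ 5 = 43%.
- Baseline 15, rise 10: (17.03 − 14.89) ÷ 10 = 2.14 ÷ 10 = 21%.

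Rises of 5 and 10 mmHg give almost the same treated mean, while the escalation count separates them. In this model a step is added only when a reading reaches 25 mmHg, so the number of readings at or above 25 equals the number of escalations. A threshold summary of the trace would therefore recover the signal here. It would miss steps taken before 25 mmHg is reached, which is why both summaries are useful.

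**The case against.** The strongest reply is that the gap is narrow, and much of that reply stands.

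- Daily mean ICP is not the only route by which a problem could surface. Worsening of a pre-existing condition is an adverse event under section 1, and section 1.6 extends reporting to any safety assessment. Patients who accept microdialysis also have brain glucose, lactate:pyruvate ratio, glutamate and glycerol outcomes. But with no ICP trigger named, adverse event capture depends on judgement in patients who may already be receiving ICP therapy, and microdialysis is optional within a subset.
- A reader might infer that the planned endpoint would show nothing of a drug-related rise. The documents do not support that. Item 6 holds ICP below a ceiling; it does not return it to its prior level. A rise from 15 to 20 mmHg that prompts no therapy would appear in full in the mean.
- A reader might also infer that no summary of the pressure trace could help. That is too strong: the target is a threshold and the trace is continuous, so episodes or time at or above 25 mmHg would capture many of the rises that lead to escalation.
- For CPP the argument is weaker. The documents state no CPP target and no vasopressor protocol, and section 10.2 already counts hypotensive episodes. It remains true that pressures are read under whatever support is being given.
- With no control group, escalation cannot be separated from the course of the injury. In the illustration 40% of patients at baseline 18 were escalated with no rise at all. The same limit applies to daily mean ICP, so it is a reason for cautious wording rather than for leaving the therapy out.

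**Conclusion.** The concern holds in a limited form. The only ICP-specific outcome is a mean measured under therapy directed at ICP, and the recorded therapy is not analysed. Rises met by escalation can be partly or largely masked: on the assumed inputs between 3% and 43% of the rise stays visible in the day-2 mean. These percentages depend on the assumed baseline, variability, step effect and non-withdrawal of steps, and none of them estimates what this trial would see.

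A reader might go on to infer that the decision about a later efficacy trial is compromised. It is not: the three feasibility criteria concern severe hypoglycemia, reaching the glucose goal, and nausea leading to discontinuation. ICP and CPP are descriptive endpoints in a single-arm study of 24 completers, of whom an unstated number will have ICP monitoring. This is a worthwhile low-priority improvement to the description, and no sample size change follows.

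**What to change.** In section 10.2, for patients with ICP monitoring, add the following beside daily mean ICP and CPP and state the number of patients contributing:

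- the highest recorded ICP management step on each day of infusion;
- the number and proportion of patients escalated after the start of exenatide, relative to the step in place just before it;
- the number of episodes, or the time, at or above 25 mmHg from the continuous trace;
- vasopressor use during infusion, from the recorded medications.

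State in item 12 that these summaries are descriptive and will not be read as effects of exenatide. No treatment target or clinical rule changes.

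The cost is modest but not zero. The documents do not define the steps, so an ordered coding has to be written before the data are examined. The therapy level and vasopressor use just before infusion must be abstracted from the chart, because baseline recording is stated for ICP values but not for therapy. A definition of an episode (minimum duration and gap) is also needed for the trace summary.
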